#### 6.2.2. Primary Analysis

The primary efficacy variable for this study is the change from baseline to week 4 in the weekly average of the daily average NRS pain scores. This variable will be analyzed using a Mixed Model Repeated Measures (MMRM) model with change from baseline in the weekly average of the daily average NRS scores at weeks 1, 2, 3 and 4 as the dependent variable; week, pooled study center, treatment, and treatment by visit interaction as fixed factors, baseline weekly average of the daily average NRS scores as covariate; and patient as a random effect. The unstructured covariance matrix for repeated observations within patients will be used. If the model does not converge, the maximum-likelihood (ML) estimation method will be used instead of the default restricted ML (REML) method. If the model still does not converge, then simpler covariance structures with less parameters will be used in the following order until the model does converge: heterogeneous autoregressive (1) (ARH[1]); heterogeneous compound symmetry (CSH); autoregressive (1) (AR[1]); and compound symmetry (CS). The primary treatment comparison will be conducted at week 4 in this model.

The least square (LS) means and standard error of each treatment group, LS means differences including standard error, 95% confident interval (CI) and p-values, between each active group and the placebo group for the change from baseline to weeks 1, 2, 3 and 4 in the weekly average of the daily average NRS pain scores will be presented in the tables.

SAS code for primary endpoint:

```

Proc mixed data=datain;
Class treatment week patient;
Model change=base treatment center week treatment*week/ddfm=kr;
Repeated week/sub=patient type=un;
Lsmean treatment*week/pdiff cl ;
*** treatment order in the data will be placebo, 4%, 8%*****;

Estimate '4% vs. Placebo at week 4' treatment -1 1 0 treatment*week 0 0 0 -1
0 0 0 1 0 0 0 0/ cl;
Estimate '8% vs. Placebo at week 4' treatment -1 0 1 treatment*week 0 0 0 -1
0 0 0 0 0 0 1/cl;

Run;

```

A descriptive summary of the weekly average of the daily average NRS pain scores at baseline, weeks 1, 2, 3 and 4, as well as the change from baseline will be provided by treatment group.

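### SAP 6.2.2: the sample code's 8% versus placebo contrast at week 4 is one coefficient short and not estimable, although the prose and the LS-means line specify the right comparison

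*SAP*

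**What the plan says.** SAP 6.2.2 fits an MMRM with the change in "scores at weeks 1, 2, 3 and 4 as the dependent variable" and then states: "The primary treatment comparison will be conducted at week 4 in this model". It also says that LS mean differences from placebo, with standard errors, confidence intervals and p-values, will be tabulated for each active group at all four weeks.

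The sample program that follows has these relevant lines:

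- the class statement, "Class treatment week patient";
- the model statement, "Model change=base treatment center week treatment*week/ddfm=kr";
- an LS-means request, "Lsmean treatment*week/pdiff cl";
- a comment fixing the level order, "treatment order in the data will be placebo, 4%, 8" (the last level being the 8% arm);
- the low-dose contrast, "Estimate '4% vs. Placebo at week 4' treatment -1 1 0 treatment*week 0 0 0 -1", continued on the next line by `0 0 0 1 0 0 0 0`;
- the high-dose contrast, "Estimate '8% vs. Placebo at week 4' treatment -1 0 1 treatment*week 0 0 0 -1", continued on the next line by `0 0 0 0 0 0 1`.

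Neither contrast gives coefficients for the week main effect.

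**The concern.** The two contrasts should have the same form: each dose minus placebo, both at week 4. They do not have the same number of coefficients. If the high-dose line is one short, its last coefficient sits one cell too early and the statement cannot deliver the comparison in its label.

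These are the only two labelled contrasts in the primary-endpoint program, and the affected one is for the higher dose. SAP 2.5.2 keeps the randomization codes blinded until the SAP is approved and the database is locked. If the fault is found only when the program is run on unblinded data, the primary code has to be repaired after unblinding. That is easily avoided.

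**Working it through.** **Inputs (all SAP 6.2.2).** Treatment has 3 levels, in the order placebo, 4%, 8%. Week has 4 levels. Treatment precedes week in the class statement, so week varies fastest within treatment. The interaction therefore has 3 × 4 = 12 cells, and the cell number is 4 × (treatment position − 1) + week.

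**Low-dose contrast first, as the benchmark.** 4 + 8 = 12 coefficients.
- The −1 is in cell 4 = 4 × 0 + 4, placebo week 4.
- The +1 is in cell 8 = 4 × 1 + 4, 4% week 4.

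This matches its label and confirms the cell order.

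**High-dose contrast as printed.** 4 + 7 = 11 coefficients.

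| | Placebo, weeks 1–4 | 4%, weeks 1–4 | 8%, weeks 1–4 |
|---|---|---|---|
| 4% line | 0 0 0 −1 | 0 0 0 1 | 0 0 0 0 |
| 8% line, printed | 0 0 0 −1 | 0 0 0 0 | 0 0 1 (none given) |
| 8% line, needed | 0 0 0 −1 | 0 0 0 0 | 0 0 0 1 |

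The +1 is in cell 11 = 4 × 2 + 3, which is 8% week 3. The target is cell 12 = 4 × 2 + 4.

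**Estimability.** Write τ for treatment, ω for week and γ for interaction effects. The printed line asks for

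τ(8%) − τ(placebo) + γ(8%, week 3) − γ(placebo, week 4).

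Add any constant k to ω(week 3) and subtract k from the three week 3 interaction terms. Every fitted mean is unchanged, but the quantity above changes by −k. The model therefore does not determine it, and it is not estimable. Equivalently, the interaction coefficients sum to +1 at week 3 and −1 at week 4, while the week coefficients are all 0. In the 4% line they sum to 0 at every week.

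**Numerical check.** I built the over-parameterised design matrix X for 330 patients × 4 weeks, with made-up baseline and centre values, and tested whether L(X′X)⁻(X′X) = L. Largest departures:

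| Contrast | Centre continuous (as coded) | Centre as 15-level class factor |
|---|---|---|
| 4% as printed | about 5 × 10⁻¹⁵ | 0.0001 |
| 8% as printed | 0.25 | 0.25 |
| 8% with the added zero | about 3 × 10⁻¹⁵ | 0.0002 |
| 8% as printed plus `week 0 0 1 -1` | about 2 × 10⁻¹⁵ | 0.0003 |

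The small values in the last column are rounding in the generalised inverse. The algebra above is exact and does not involve centre. The last row is estimable, but it compares 8% at week 3 with placebo at week 4, so adding week coefficients would be the wrong repair.

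**The case against.** The strongest answer is that nothing reported has to depend on this line. The prose defines the week 4 comparison correctly and promises LS mean differences for each dose. The LS-means request in the same program produces those differences without using the contrast coefficients. No sentence in the SAP makes the contrast output the reported result. This stands, and it is why the severity is limited.

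The failure is also visible. A non-estimable contrast returns no estimate, so an empty 8% row would appear beside a populated LS-means table. This also stands.

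A reader might infer more: that the trial would report 8% at week 3 against placebo at week 4 under a week 4 label, or that the two doses would be compared with placebo on different footings. The documents support neither. The first needs someone to add week coefficients, which appear nowhere in the SAP. The second overlooks the LS-means line, which treats both doses alike.

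A zero may have been lost when the PDF was read into text, because the point rests on one character in a run of zeros after a line break. The neighbouring 4% line kept all 12 coefficients, so a real slip is plausible, but only the SAP page can settle it.

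Finally, the added zero does not make the whole program match the text. Centre is in the model statement but not in the class statement, so it would be fitted as a continuous covariate although the prose calls it a fixed factor. That is a separate fault. It affects the LS-means differences and the 4% contrast too, and it does not alter the result here.

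**Conclusion.** The point holds as a code error of minor to moderate severity. As printed, one of the two labelled primary contrasts has 11 coefficients where 12 are needed, places its +1 on 8% week 3, and is not estimable. The estimand, the significance level, the power and the 4% contrast's coefficients are untouched, and the correct 8% difference is already requested in the same program.

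This rests on three assumptions:

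- **The printed page matches the text.** If the page shows the twelfth coefficient, the coefficient error disappears.
- **The level order is as the program states.** The mixing of weeks does not depend on this, because cell 11 is week 3 of whichever treatment comes third.
- **The software sets an omitted trailing coefficient to zero and reports a non-estimable contrast as having no estimate.** This is my understanding of PROC MIXED; the documents do not state it.

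**What to change.** Check the SAP page. If the zero is missing there, change the high-dose line to

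`treatment -1 0 1 treatment*week 0 0 0 -1 0 0 0 0 0 0 0 1 / cl`

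Add one sentence to SAP 6.2.2 stating that the reported primary comparisons are the week 4 LS-means differences of each dose from placebo, and that both contrasts must equal them. That makes the contrasts a built-in check on the program and settles which output is reported.

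The cost is one character and one sentence, made before unblinding. No design, sample size or analysis choice changes. The class statement can be reconciled with the prose on centre in the same edit.

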### 6.2.3. Sensitivity Analysis

Two sensitivity analyses will be performed in order to assess the robustness of the results of the primary analysis to changes in the assumptions and data characteristics. The first sensitivity analysis is a multiple imputation method to handle missing weekly average of the daily average NRS pain scores for week 4. Consistent with the recommendations of the National Academy of Sciences report (National Research Council 2010), under the assumption of missing at random (MAR) and taking into account of potential bias towards the active arm for patients who withdrew from the study due to adverse events, the following steps will be carried out in SAS using the MI, Mixed, and MIANALYZE procedures:

- Step 1: prepare data set for MI procedure (PROC MI)

The following auxiliary variables are to be included in the model for PROC MI:

- Treatment (1=placebo, 2=TV45070 4%, 3=TV45070 8%)
- R1150W genotype (1=AA, 2=GA, 3=GG)
- All observed pain scores, screening, baseline, and weekly averages at each post randomization week (week 1, week 2, week 3, week 4)

The treatment will be coded to 1 (placebo) for those in the active arms withdrawn from study due to an adverse event or lack of efficacy. Thus, the missing week 4 pain scores will be imputed based on the observed placebo patient's data. In order to adjust for the use of rescue medication at week 4, the average weekly pain intensity at week 4 will be set to missing for patients who used an excessive amount of rescue medication during the week before the multiple imputation. Excessive use of rescue medication is defined as the use of rescue medication on at least 4 out of 7 days of the week 4 treatment.

- Step 2: run PROC MI. The following SAS code may be used to generate the imputed data sets:

```

Proc mi data=datain nimpute=5 seed=598719001 out=mi_out
  Maximum=10 minimum=0 round=0.01;
  Class treat genotype;
  Var treat genotype screening baseline week1 week2 week3 week4;
  Monotone reg;

```

Run;

Note: if the missing data pattern is not monotonic, a Markov Chain Monte Carlo (MCMC) method will be used instead of a regression method for imputing missing data. R1150W genotype will be used, with all 3 possible categories.

- Step 3: run mixed procedure (PROC MIXED) using the data from PROC MI

The output data set MI\_OUT, from the above MI procedure, will contain 5 complete data sets with the missing data points filled using the specified imputation methods, and 1 additional variable, \_IMPUTATION\_, to indicate the order of the imputed data sets. Then within each data set, the primary variable, change from baseline at week 4, will be derived by subtracting baseline from week 4. Each data set will be analyzed using the ANCOVA model with the primary variable and the dependent variables, the screening and baseline scores as covariates, pooled study center, treatment and genotype as factors in the model. The following SAS code may be used to analyze the imputed data sets.

```
ODS output diffss=mixed_out;
Proc mixed data=mi_out method=reml;
  By _imputation_;
  Class center armcd genotype;
  Model change4 = center armcd genotype baseline screening;
  Lsmeans armcd/diff;
Run;
```

ARMCD represents the treatment the patient was randomized to receive.

- Step 4: calculate overall p-value and construct 95% confidence interval for the treatment difference.

The output data from the above SAS code will contain the estimate of the mean difference and the standard error of the estimate from each of the 5 data sets. The SAS procedure mianalyze (PROC MIANALYZE) will be used to generate an overall p-value and 95% confidence interval for the treatment difference. The following SAS code may be used.

```
ODS output parameterestimates=parmest;
Proc mianalyze data=mixed_out alpha=0.05 theta0=0;
  Model effects estimate;
  Stderr stderr;
Run;
```

The second sensitivity analysis will be similar to the first one except that the baseline observation carried forward (BOCF) method will be used to impute the missing week 4 weekly average of the daily average NRS pain scores for those who discontinued the study early due to adverse event or lack of efficacy. Details for the week 4 imputation methods for missing weekly average of the daily average NRS pain scores for the two sensitivity analyses are given in [Table 2](#) below.

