## **2.3. Sample Size and Power Considerations**

In prior studies of gabapentin or pregabalin treatment of PHN, the difference in mean pain scores between active- and placebo-treated groups ranged from 1.0 to 1.3. For this study, a conservative estimate of 1.0 will be used. Assuming a standard deviation of 2.35, a sample size of 88 per arm (a total of 264 patients) would be needed to provide 80% power with a 2-sided test at 5% significance level to detect a 1.0-point difference. Assuming an approximately 20% dropout rate, 110 patients per arm (a total of 330 patients) will be randomly assigned to each treatment group.

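### SAP 6.2.3 pools only 5 imputations, which leaves avoidable Monte Carlo error in the sensitivity estimate and p-value; raising the number is a minor, free improvement

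*SAP*

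**What the plan says.** SAP 6.2.3 (Sensitivity Analysis) gives the imputation call as "Proc mi data=datain nimpute=5 seed=598719001 out=mi_out". The text then says that the output "will contain 5 complete data sets with the missing data points filled using the specified imputation methods", and its Step 4 again refers to estimates from each of the 5 data sets. PROC MIANALYZE "will be used to generate an overall p-value and 95% confidence interval for the treatment difference".

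The imputation model contains treatment, genotype and "All observed pain scores, screening, baseline, and weekly averages at each post randomization week". Besides dropout, the SAP creates missing values itself: "the average weekly pain intensity at week 4 will be set to missing for patients who used an excessive amount of rescue medication". Excessive means rescue use on at least 4 of the 7 days. SAP 2.3 plans for the loss of about a fifth of patients: "Assuming an approximately 20% dropout rate, 110 patients per arm (a total of 330 patients) will be randomly assigned to each treatment group".

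SAP Table 2 uses multiple imputation in both sensitivity analyses. In Sensitivity 2, however, patients who stop for an adverse event or lack of efficacy get their baseline value instead. The code is offered permissively ("The following SAS code may be used to generate the imputed data sets"), but the prose states five data sets without qualification. The SAP gives no reason for five, no Monte Carlo error criterion and no rule for raising the number.

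**The concern.** Multiple imputation fills gaps with random draws, so the pooled estimate and p-value depend partly on those draws. With few imputations that part is not small. The two sensitivity analyses are there to show whether the primary result holds up under other treatments of missing data. If the stable answer lies near 0.05, a pooled p-value from five imputations may fall clearly on either side of it for reasons unrelated to the data. There are two doses and two analyses, so four such p-values. SAP 6.1 sets a two-sided 5% level for all testing, and SAP 4.3 makes no multiplicity adjustment.

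**Working it through.** **The plan's own figures.** SAP 2.3 gives SD 2.35, difference 1.0, two-sided 5% and 80% power.

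- Normal approximation: n = 2(1.96 + 0.842)² × 2.35² / 1.0² = 86.7, so 87 per arm. Exact t-test power is 79.7% at 87 and 80.2% at 88, so the stated 88 is reproduced.
- Dropout: 88 / 0.80 = 110 per arm, as stated.

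The documents give no figure for Monte Carlo error or for the fraction of missing information (FMI), so FMI is varied below.

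**Formulas.** Let W be the average within-imputation variance, B the between-imputation variance and m the number of imputations. Rubin's rules give

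- T = W + (1 + 1/m)B, r = (1 + 1/m)B/W, df = (m − 1)(1 + 1/r)².
- For fixed data, the pooled estimate varies over seeds with SD √(B/m).
- With FMI = B/(W + B), that SD in units of the standard error is √(FMI/m).

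**Hand check.** At FMI 0.20 and m = 5 the SD is √(0.20/5) = 0.20 standard errors. A stable z of 1.96 then ranges over 1.96 ± 1.96 × 0.20, or 1.57 to 2.35, which is p from 0.117 down to 0.019. At m = 100 the SD is √(0.20/100) = 0.045 standard errors.

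In NRS points, take the standard error as 2.35 × √(2/88) = 0.354. The SD over seeds at m = 5 is then 0.050 (FMI 0.10) to 0.071 (FMI 0.20). At m = 100 it is 0.011 to 0.016.

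**Full check.** The hand check leaves out that B, and with it the degrees of freedom, is itself poorly estimated from five values. Including this (estimate drawn from a normal with variance B/m, B from a scaled chi-square on m − 1 df, stable p = 0.05) gives these central 95% ranges of the p-value over seeds:

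| FMI | m = 5 | m = 20 | m = 50 | m = 100 |
|---|---|---|---|---|
| 0.09 | 0.026–0.102 | 0.036–0.070 | 0.041–0.062 | 0.043–0.058 |
| 0.10 | 0.024–0.106 | 0.035–0.072 | 0.040–0.063 | 0.043–0.059 |
| 0.15 | 0.020–0.131 | 0.032–0.079 | 0.038–0.067 | 0.041–0.061 |
| 0.20 | 0.016–0.155 | 0.029–0.086 | 0.036–0.070 | 0.039–0.064 |

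**Which FMI is plausible.** The Sensitivity 1 procedure was simulated with 3 × 110 patients, monotone dropout, sequential regression imputation bounded to 0–10, and half of the dropouts recoded to placebo (an assumption). The ANCOVA used 15 pooled centers, genotype, baseline and screening. Data sets with p near 0.05 were re-imputed 600 times at m = 5.

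- 20% dropout, week-to-week correlation 0.5 to 0.9: FMI about 0.09 to 0.15. The central 95% range had a lower end of 0.019 to 0.025 and an upper end of 0.106 to 0.129.
- 30% missing at week 4 (for example dropout plus heavy rescue use): FMI about 0.19 to 0.20, range about 0.017 to 0.15–0.16.
- Over all these settings, about 40% to 53% of seeds gave p < 0.05 on the same borderline data.

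**Away from the threshold.** At the planned effect, z = 1.0/0.354 = 2.82 and p is about 0.005. With m = 5 and FMI 0.09 to 0.20, at least 99% of seeds then give p < 0.05. At a stable p of 0.01 the share is 96% to 99.9%, and at 0.15 it is below 1%.

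**Over all trials.** With the planned effect, 80% power and FMI 0.10 to 0.20, the verdict at 0.05 from m = 5 differs from the verdict with unlimited imputations in about 4% to 7% of comparisons. At m = 100 it differs in about 1%. With no effect, the figure at m = 5 is about 2%.

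**The case against.** The strongest reply is that nothing here is wrong, only noisy. A reader might infer that the result can be changed by choosing another seed. The documents do not support that: the seed is written into the SAP, so following the code gives one reproducible number. The permissive wording around the code loosens this a little, but the SAP plans no reseeding. What remains is that a fixed seed freezes one draw without removing its error.

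A reader might also infer that five imputations make the p-value invalid. They do not. The (1 + 1/m)B term and the reduced degrees of freedom allow for the small number: type I error in the check is 0.05 at m = 5, and power is 0.77 to 0.79 against 0.80. The loss is in precision and stability.

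It is tempting, too, to say that the robustness verdict as such depends on the seed, or to quote one p-value range without conditions. The movement matters only near 0.05, and its width rests on an assumed FMI. The weekly scores in the imputation model recover information, so FMI is probably below the dropout rate unless heavy rescue use adds much missing data.

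The figures should not be applied to Sensitivity 2. Baseline values replace part of the imputation there, so its range should be narrower; it was not computed. The primary MMRM in SAP 6.2.2 uses no imputation, and no passage of the two documents ties a go/no-go rule to a sensitivity p-value. All of this limits the point; none of it is a reason to keep five.

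**Conclusion.** The point holds as a minor one. For a stable p of about 0.05, the Sensitivity 1 p-value has a central 95% range over possible seeds of about 0.025 to 0.10 at FMI 0.09, widening to 0.016 to 0.16 at FMI 0.20. One hundred imputations reduce this to about 0.04 to 0.06. Both the borderline p and the FMI are assumptions, and the 20% dropout is the plan's forecast. The documents do not support a claim of invalid inference, of an open seed, or of a primary or clear result at risk. They do support saying that an analysis meant to test robustness carries random error that costs almost nothing to remove.

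**What to change.** In SAP 6.2.3, change nimpute=5 to nimpute=100 and keep the prespecified seed. Change both statements about 5 data sets (the description of MI_OUT and the text of Step 4) to match. The documents imply no particular number; 100 is proposed because it brings the range to about 0.04 to 0.06 over the FMI values considered, where 50 would leave about 0.04 to 0.07. It would also help to report the Monte Carlo standard error, √(B/m), beside each pooled estimate.

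The model, data and hypothesis stay as they are. SAP 2.5.2 requires SAP approval before unblinding, so the edit belongs before that approval. The cost is negligible computing time.

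### Sensitivity Step 4 plans one treatment difference for a two-dose trial, and its code pools three arm differences as one; the primary code omits center from CLASS

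*SAP*

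**What the plan says.** **Primary analysis (SAP 6.2.2).** The text promises LS mean differences with confidence intervals and p-values "between each active group and the placebo group for the change from baseline to weeks 1, 2, 3 and 4". That is two comparisons, and the code has one ESTIMATE row for each, written as active minus placebo. The model text lists "week, pooled study center, treatment, and treatment by visit interaction as fixed factors". The code opens with "Class treatment week patient" and puts center in the MODEL statement only.

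**Sensitivity analysis (SAP 6.2.3).** Step 3 fits an ANCOVA to each of 5 imputed data sets and requests "Lsmeans armcd/diff", where ARMCD is the randomized arm. Step 4 says the output "will contain the estimate of the mean difference and the standard error of the estimate from each of the 5 data sets", and that PROC MIANALYZE "will be used to generate an overall p-value and 95% confidence interval for the treatment difference". The MIANALYZE code takes the whole output data set, with no BY statement and no selection of rows. The code blocks are offered as optional; the sentence on MIANALYZE is a commitment. For the other analysis: "The second sensitivity analysis will be similar to the first one except that the baseline observation carried forward (BOCF) method will be used".

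Table 2 of the SAP gives imputation rules only, and the list of summaries (SAP 12.1, table 15.2.1.3) names no comparison.

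**The concern.** The two sensitivity analyses are there to show whether the primary result for each dose survives other assumptions about missing data. Step 4 does not say which dose its single difference refers to, and the suggested code cannot return either dose-placebo difference. Once the misprinted names are corrected, the code would run and give one plausible-looking row. That row could not be set beside the primary result for 4% or for 8%, and the comparison might then be chosen after unblinding.

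The center slip is a separate fault: followed literally, the primary program does not fit the model the text describes. The secondary ANCOVA code (SAP 6.3.2) and the sensitivity ANCOVA code both list center in CLASS, so the omission looks accidental.

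**Working it through.** **Inputs from the SAP.** Three arms, 1:1:1 (2.4); effect 1.0, SD 2.35, 88 per arm needed and 110 randomized (2.3); two-sided 5% tests (6.1); 5 imputations (6.2.3); about 15 pooled centers (4.6).

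**Assumed.** ARMCD sorts placebo, 4%, 8%. The SAP uses that order for its treatment variable (6.2.2 and 6.2.3 Step 1) but does not state it for ARMCD. The between-week correlation (0.5 to 0.8) and the center intraclass correlation, ICC (0 to 0.20), are not in the documents, so ranges are used. No SAS was run; the figures take the two misprinted SAS names as corrected and nothing else as changed.

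**The plan's own figure.** n = 2 × (1.960 + 0.842)² × 2.35² / 1.0² = 86.7, so 87 per arm by the normal approximation. The t-based power at 88 is 80.2%, and 88 / 0.80 = 110. The sample size reproduces and is not in dispute.

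**What the code pools.** Three arms give three pairwise differences; 3 × 5 = 15 rows. With arm means m1, m2, m3 in sort order, the pooled estimate is

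[(m1 − m2) + (m1 − m3) + (m2 − m3)] / 3 = (2/3)(m1 − m3).

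The middle arm cancels. This is algebra and rests on no assumed effect.

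**Rubin's rules on the 15 rows** (both doses 1.0 better, 110 per arm, no imputation noise; differences 1, 1, 0, each five times):
- Estimate: 2/3 = 0.67
- Within variance: 2 × 2.35² / 110 = 0.1004
- Between variance: [10 × (1/3)² + 5 × (2/3)²] / 14 = 0.2381
- Total: 0.1004 + (16/15) × 0.2381 = 0.3544, so SE 0.595
- df = 14 × (1 + 0.1004/0.2540)² = 27.3; t = 0.667/0.595 = 1.12; p = 0.273

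The spread between different comparisons has been counted as imputation uncertainty. Done per dose: 1.0, SE = √0.1004 = 0.317, 95% CI 0.38 to 1.62, p = 0.002. At 88 per arm the pooled row has SE 0.616 and p = 0.287, against SE 0.354 and p = 0.005 per dose.

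**Pooled estimate by ARMCD order** (placebo mean change 0, an effective dose −1):

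| Truth | placebo, 4%, 8% | 4%, 8%, placebo | 4%, placebo, 8% |
|---|---|---|---|
| Both doses work | 0.67 | −0.67 | 0.00 |
| Only 4% works | 0.00 | −0.67 | −0.67 |
| Only 8% works | 0.67 | 0.00 | 0.67 |

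No order yields the result for either dose.

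**With imputation simulated** (2,000 trials per scenario, 330 patients, 20% random monotone dropout, 5 regression imputations, order placebo, 4%, 8%). Share of trials with p<0.05:

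| Truth | 15-row pool | 4% vs placebo | 8% vs placebo |
|---|---|---|---|
| Both doses work | 0.5–0.6% | 81–86% | 80–85% |
| Only 4% works | 0% | 83–85% | 5% |
| Only 8% works | 0.4–0.6% | 5% | 82–85% |

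**Sign.** With placebo first, the LSMEANS rows are placebo minus active, the reverse of the primary ESTIMATE rows.

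**Center.** As a factor, 15 centers use 15 − 1 = 14 df. As a numeric covariate, center uses 1; a character code stops the run. SE of the treatment difference at 88 per arm (3,000 simulated trials per ICC, single week 4 model, 15 equally likely centers):

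| ICC | Factor | Slope |
|---|---|---|
| 0 | 0.364 | 0.355 |
| 0.02 | 0.360 | 0.354 |
| 0.05 | 0.355 | 0.354 |
| 0.10 | 0.346 | 0.352 |
| 0.20 | 0.325 | 0.350 |

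At ICC 0.20 power is 0.86 with the factor and 0.80 with the slope. The mean estimate is within 0.01 of the true −1.00 in every case.

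**The case against.** The strongest reply is that the Step 3 and Step 4 code is optional, and that a programmer who corrects the misprinted names would also notice 15 rows where the text speaks of 5 data sets. The intended comparisons can be inferred: these analyses check the primary result, the primary result is each dose against placebo, and nothing in the SAP suggests combining doses. On that reading the singular is loose wording. This limits the severity but does not remove the fault, because the committed sentence names no comparison and nothing else in 6.2.3 supplies one.

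Three smaller points stand. The simulation uses random dropout and compares arms at week 4; it omits the recoding of some active-arm withdrawals to placebo and the removal of week 4 scores after heavy rescue use. The 80% to 86% therefore illustrates correct pooling and is not the power of the planned analysis. The sign matter is one of labelling, since the LS means output of the primary program runs in the same direction. And the center slip is mild: the text is clear, a character code would be caught at once, and up to an ICC of 0.05 the slope coding costs no precision.

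**Conclusion.** The point holds. Step 4 leaves its target undefined, and its code, followed as printed after correcting two names, returns (2/3)(first arm − last arm), which is neither dose-placebo difference. That follows for any data. The size shown, 0.67 with p = 0.27 against 1.0 with p = 0.002, assumes both doses 1.0 better, SD 2.35, 110 per arm, no imputation noise and the order placebo, 4%, 8%; the other orders are also wrong. Both sensitivity analyses are affected.

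The primary code also differs from the primary model in the text. This brings no bias, and the effect on precision is small unless centers differ a good deal. Both items should be corrected before unblinding. Neither touches the sample size, and the Step 4 fault does not touch the primary result.

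**What to change.** 1. Reword Step 4 so that it pools each of two differences, 4% minus placebo and 8% minus placebo, across the 5 imputations. State the ARMCD order. Keep only those two rows per imputation, set the sign to active minus placebo (multiply by −1 if placebo sorts first), sort by comparison, and run PROC MIANALYZE by comparison. Say that the same applies to the BOCF analysis.
2. Change the primary statement to `Class treatment week patient center;`.
3. Check three items on the original SAP page, since they may be losses in text extraction: whether the 8% ESTIMATE row has 12 treatment-by-week coefficients (11 appear in the text, against 12 for 4%), the ODS table name printed as `diffss`, and the MIANALYZE statement printed as `Model effects`. The 8% comparison is in any case available from the LSMEANS output.

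The cost is two sentences and a few lines of SAS. No data collection or patient is affected.
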